8.3.2. Prior Drug Treatments for Psoriatic Arthritis

Prior drug treatment will include any treatment for PsA prior to the first dose of study medication in Study A3921092. It will include the drug treatment prior to the qualifying study, the treatment used during the qualifying study (which includes adalimumab but not tofacitinib) and any treatment used during the enrollment gap between the qualifying study and the Study A3921092.

- Prior DMARDs (disease-modifying antirheumatic drugs) drug treatment (yes, no), yes is defined for a subject who used any DMARDs;
- Prior bDMARDs (biologic DMARD) drug treatment (yes, no), yes is defined for a subject who used any bDMARDs;
- Prior TNFi (Tumor necrosis factors inhibitor) bDMARDs drug treatment (yes, no), yes is defined for a subject who used any TNFi bDMARDs;
- Prior non-TNFi bDMARDs drug treatment (yes, no), yes is defined for a subject who used any non-TNFi bDMARDs;
- Prior csDMARDs drug treatment (yes, no), yes is defined for a subject who used any csDMARDs;
- Prior non-DMARDs drug treatment (yes, no), yes is defined for a subject who used any non-DMARDs;
- Prior oral corticosteroids use (yes, no);
- Prior NSAIDs use (yes, no).

8.3.3. Concomitant Drug Treatments for Psoriatic Arthritis

Concomitant drug treatment will include any treatment for PsA during Study A3921092.

- DMARDs drug treatment (yes, no);
- Non-DMARDs drug treatment (yes, no);
- Oral corticosteroids use (yes, no);
- NSAIDs use (yes, no);
- Joint injection drug use (yes, no).

10. APPENDICES

Appendix 1. Definition and Use of Visit Windows in Reporting

For reporting purposes, the following visit windows will be used for efficacy/PRO variables and for any safety displays that display by week/month. If two or more visits/observations fall into the same window, the visit/observation closest to the target day should be used in the analyses. If there is a tie, the later visit should be used. However, if two or more visits/observations fall in the same window, and the latest visit is the last visit of the study due to early termination, then this will be the visit used in the analysis for that visit window. Per the master visit schedule provided to the investigator sites, a month is defined as 4 weeks or 28 days.

Study day will be calculated as: date of assessment/collection – date of the first dose + 1.

Visit Label	Target Day	Definition [Day Window] - Lower	Definition [Day Window] - Upper
Screening		Prior to baseline visit	
Baseline		
The baseline values for the safety endpoints come from the baseline of the qualifying study for patients who enroll within 14 days of the last visit of the qualifying study. For the patients whose enrollment are out of 14-day window, their baseline values of the safety endpoints will be from the baseline visit of this study, A3921092.
 
The baseline values for all the efficacy or health-outcome endpoints come from the baseline of the qualifying study.
 
In addition, in the sensitivity analysis for the ACR response rates and ΔHAQ-DI, the baseline value will be the baseline visit for A3921092 for subjects whose enrollment is out of 14-day window.
 
Day 1 = date of first dose of study treatment taken of study A3921092.
	
Month 1	29	1*	57
Month 3	85	58	127
Month 6	169	128	211
Month 9	253	212	295
Month 12	337	296	379
Month 15	421	380	463
Month 18	505	464	547
Month 21	589	548	631
Month 24	673	632	715
Month 27	757	716	799
Month 30	841	800	883
Month 33	925	884	967
Month 36	1009	968	1051 (for safety) ≥969 (for efficacy and PRO)
Month 39**	1093	1052	1135
Month 42**	1177	1136	1219
Month 45**	1261	1220	1303
Month 48**	1345	≥1304	

*The lower limit of the Month 1 visit window will be Day 2 for safety analysis for subjects who enroll out of 14-day window of the last visit of the qualifying study.

**For safety endpoints summarized by visit such as laboratory value and vital signs data at a windowed visit only.

Note some of the endpoints may not be measured at every visit. For example, SF-36v2, FACIT-F, EQ-5D-3L, PsA-HCRU, WLQ, DLQI, NAPSI and ISI will not be assessed at Months 3 per the study protocol and the visit window at Month 3 will be undefined. In the event that an observation falls into one of the undefined visit windows, that observation will not be used in analysis.

The following categories will be used in the treatment exposure and duration of treatment summaries. The duration will be calculated as: date of the last dose – date of the first dose +

1. Any missed doses/drug holidays will be ignored in the calculation.

Category (days)
1
2-14 (2 weeks)
15-28 (2 weeks-1 month)
29-84 (1-3 months)
85-168 (3-6 months)
169-252 (6-9 months)
253-336 (9-12 months)
337-504 (12-18 months)
505-672 (18-24 months)
673-840 (24-30 months)
841-1008 (30-36 months)
1009-1176 (36-42 months)
≥1177 (42-48 months)

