7.4. Sub-study Definition and Use of Visit Windows in Reporting

The visit windows are similarly defined as for the main LTE study in below table. The study day will be calculated as: date of assessment/collection – date of the first dose in the sub-study + 1.

If two or more visits/observations fall into the same window, the visit/observation closest to the target day should be used in the analyses. If there is a tie, the later visit should be used. However, if two or more visits/observations fall in the same window, and the latest visit is the last visit of the study due to early termination, then this will be the visit used in the analysis for that visit window. Per the master visit schedule provided to the investigator sites, a month is defined as 4 weeks or 28 days.

Visit Label	Target Day	Definition [Day Window] – Lower	Definition [Day Window] - Upper
Switch/Baseline	1	Day 1 = date of first dose of study treatment taken of sub-study Prior to first dose of study treatment taken of sub-study	
Month 1	29	2	57
Month 3	85	58	127
Month 6	169	128	211
Month 9	253	212	295
Month 12	337	≥296	

The following categories will be used in the treatment exposure and duration of treatment summaries for tofacitinib. The duration of treatment will be calculated as: date of the last dose in the sub-study – date of the first dose in the sub-study + 1. Any missed doses/drug holidays will be ignored in the duration calculation. Treatment exposure will be defined as the number of days that subjects took the study drug (gaps not counted).

Category (days)
1
2-28 (1 month)
29-84 (1-3 months)
85-168 (3-6 months)
169-252 (6-9 months)
≥253 (9-12 months)

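### The LTE Month 1 window opens on Day 1 for efficacy, so a pre-dose entry value is reported as Month 1 when nothing else falls on Days 2 to 57

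*SAP*

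**What the plan says.** SAP Appendix 1 states that "the following visit windows will be used for efficacy/PRO variables and for any safety displays that display by week/month". The Month 1 row has target Day 29, lower limit Day 1 (asterisked) and upper limit Day 57. The asterisk reads: "The lower limit of the Month 1 visit window will be Day 2 for safety analysis", and it confines this to subjects enrolling more than 14 days after the qualifying study's last visit. There is no other exception.

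Day 1 is the date of the first LTE dose, and the calculation uses dates only: "Study day will be calculated as: date of assessment/collection – date of the first dose + 1". When a window holds several observations, "the visit/observation closest to the target day should be used in the analyses"; a tie goes to the later visit, and an early-termination visit that is the latest in the window takes precedence.

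On baseline, "The baseline values for all the efficacy or health-outcome endpoints come from the baseline of the qualifying study". In the sensitivity analysis of ACR response and change in HAQ-DI, "the baseline value will be the baseline visit for A3921092 for subjects whose enrollment is out of 14-day window".

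For the sub-study, SAP Appendix 6, Section 7.4 says "The visit windows are similarly defined as for the main LTE study in below table", but its Month 1 row starts on Day 2 for all variables.

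Protocol Sections 6.1.1.2 and 6.1.3 place the entry procedures before the first dose on Visit 1, Day 1. SAP Section 7 says that missing endpoint values are not imputed.

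**The concern.** An assessment made before the first LTE dose, on the date of that dose, has study day 1 and so lies inside the Month 1 window. In the main efficacy analysis it is not used as baseline, because baseline comes from the qualifying study, and no rule excludes it from Month 1. For a subject with no later value in the window it is the only candidate and is labelled Month 1.

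Such a value says nothing about one month of LTE treatment. In a late enroller it may reflect no study drug, since entry can be up to 3 months after the qualifying study's End of Study visit. In others it may reflect adalimumab or tofacitinib given in the qualifying study. The rule also in effect fills a Month 1 value that SAP Section 7 would leave missing.

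**Working it through.** **1. Reproducing the window.** Target day = 28 × month + 1, so Month 1 = 29 and Month 3 = 85. Upper limit = midpoint of adjacent targets = (29 + 85)/2 = 57. Each later lower limit is the previous upper limit + 1. With Month 1 starting at Day 1 and the safety upper limit of 1051 for Month 36, this reproduces all 16 closed windows in the table (Months 1 to 45). The window is therefore as intended; the question is only its first day.

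**2. When a Day 1 value is selected.** Its distance from target is |1 − 29| = 28 days.

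| Other observation for that endpoint | Distance from Day 29 | Value used as Month 1 |
|---|---|---|
| Days 2 to 56 | at most 27 | the later one |
| Day 57 | 28 (tie) | the later one |
| Early-termination visit, Days 2 to 57, latest in the window | any | the termination visit |
| None on Days 2 to 57, including a first visit on Day 58 or later | – | Day 1, pre-dose |

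A Month 1 visit within the protocol's ±7 days (Days 22 to 36) always wins. A value dated before the first dose has study day 0 or less and is outside the window. That includes late enrollers' entry blood samples drawn on an earlier date, which Protocol Section 6.1.1.2 allows up to 48 hours before the visit.

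**3. Who has a Day 1 LTE value.**

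| Entry route | Pre-dose LTE assessments at entry | Month 1 lower limit |
|---|---|---|
| Same day as the End of Study visit (Protocol 6.1.2) | None; only consent, registration and dispensing are added | Nothing to capture |
| Separate visit within 14 days (Protocol 6.1.3) | Pain, patient and physician globals of arthritis, HAQ-DI, joint counts, CRP, safety laboratory tests, vital signs | Day 1 for efficacy and by-visit safety |
| More than 14 days (Protocol 6.1.1.2) | Full efficacy and patient-reported battery, laboratory tests, vital signs | Day 1 for efficacy; Day 2 for safety |

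The middle group's limited set still suffices to derive ACR, PsARC, DAS28-3 (CRP), PsAJAI and DAPSA.

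**4. Sensitivity analysis.** For a late enroller with no value on Days 2 to 57, baseline and Month 1 are the same observation. Change in HAQ-DI = 0. Every ACR component changes by 0%, so the subject is a non-responder by construction.

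**5. Size.** Let m be the proportion with nothing on Days 2 to 57 and f the fraction with a Day 1 LTE entry value, taken as unrelated. The pre-dose share of Month 1 values is m·f / (1 − m + m·f). The documents give neither m nor f. Assumed ranges:

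- m = 2%, f = 10%: 0.002/0.982 = 0.20%.
- m = 5%, f = 30%: 0.015/0.965 = 1.55%.

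If the response rate among these values differs by 10 to 30 points (also assumed), the Month 1 rate moves by 0.20% × 10 = 0.02 points to 1.55% × 30 = 0.47 points. With f = 100%, which the same-day rollover route makes implausible, the share would be 2% to 5% and the shift 0.2 to 1.5 points.

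**6. With a Day 2 lower limit.** The subject in the last row of the first table has no Month 1 value. Every other selection is unchanged.

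**The case against.** The strongest defence is that the footnote is deliberate. It sets Day 2 exactly where the LTE entry visit is the safety baseline, so that a baseline value cannot double as Month 1. Elsewhere baseline is in the qualifying study, and an LTE Day 1 value is formally post-baseline. On this view the sub-study is no benchmark: its baseline is the latest value before the first sub-study dose, so Day 2 is needed there for the same reason.

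That explains the design and it stands in part: the sub-study table alone does not prove the LTE table wrong. But the same logic requires Day 2 in the ACR and HAQ-DI sensitivity analysis, where the LTE visit is the baseline for late enrollers, and the footnote covers safety only. Nor does being post-baseline make a pre-dose value a Month 1 result.

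Four stronger readings are tempting, and the documents do not support them:

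- A reader might infer that Day 1 values compete with real Month 1 visits. The selection rules prevent this.
- A reader might equate the share of pre-dose Month 1 values with the share of missed Month 1 visits. Same-day rollovers have no LTE Day 1 assessment, and separate-visit subjects within 14 days have only a limited set of measures.
- A reader might assume that these values are all drug-free. Protocol Section 1.2.2.3 shows that qualifying-study subjects included tofacitinib arms, and that placebo subjects moved to tofacitinib at Month 3.
- A reader might think that a test or the main safety analysis is exposed. The LTE has no hypotheses, and the incidence rates in SAP Section 8.2.1 count from first dose without these windows. By-visit laboratory change, which belongs to a primary endpoint, is touched, but only descriptively and only in separate-visit subjects enrolled within 14 days.

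**Conclusion.** The point holds in a narrow form. As written, the LTE rules report a pre-dose value as Month 1 when three conditions meet: a separate LTE entry visit dated on the day of first dose, an endpoint collected at that visit, and no observation of that endpoint on Days 2 to 57. The clearest internal fault is the late-enroller sensitivity analysis, where one value serves as both baseline and Month 1.

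The effect is small: about 0.2% to 1.6% of Month 1 values and under half a point on a response rate, under the assumptions in step 5, which the documents can neither confirm nor refute. The direction is not fixed. An off-drug value in a late enroller would probably understate response, while a value carried over from effective qualifying-study treatment need not. Only descriptive Month 1 summaries are affected. This is a minor correction, worth making because it is nearly free.

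**What to change.** In SAP Appendix 1, set the Month 1 lower limit to Day 2 for all LTE endpoints and all subjects, and delete the footnote, which then has no purpose. Alternatively, keep the table and state that values obtained before the first LTE dose are not eligible for Month 1; this wording would retain any unscheduled post-dose observation on Day 1.

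Either way, the affected subjects become missing at Month 1, in line with SAP Section 7. The first option costs one digit and a footnote. The protocol schedules no assessment after dosing on Day 1, so no planned on-treatment data are lost.

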3. SUB-STUDY DESIGN

This sub-study within Study A3921092 is a Phase 3, randomized, double-blind, placebo-controlled, parallel group estimation study designed to assess the efficacy, safety and tolerability of tofacitinib 5 mg BID versus tofacitinib 5 mg BID in combination with concomitant MTX in subjects with active PsA. Subjects with active PsA will have previously completed at least 24 months of treatment with tofacitinib in Study A3921092 and will be on a stable dose of tofacitinib 5 mg BID for at least 3 months prior to the first dose of sub-study drug and be on a stable dose of oral MTX at least 4 weeks prior to the first dose of sub-study drug. This sub-study will be referred to as A3921092 Sub-study. For subjects who are

qualified to enter into the sub-study, the Combined A3921092 Sub-study Switch/Baseline visit will occur at a scheduled study visit at or after Month 24 of A3921092. There will be no separate Baseline visit for the sub-study. The visit window will remain as in the LTE in which a month is considered 28 days. Once a subject enters the sub-study, they will complete their participation in the sub-study portion and be unable to re-enter the main study. Subjects may be discontinued from the sub-study at any time during the sub-study in the event of deterioration of response as determined by the investigator.

Eligible subjects from study A3921092, will be randomized into A3921092 sub-study in a 1:1 ratio to tofacitinib 5 mg BID + MTX placebo or tofacitinib 5 mg BID + MTX. MTX will be blinded to the subjects, investigators and the sponsor. The subjects in the tofacitinib 5 mg BID + MTX group will receive blinded MTX capsules (range dose of 7.5-20 mg a week based upon the pre-existing dose) and the subjects in the tofacitinib 5 mg BID group will receive the matching MTX placebo capsules. For the duration of the sub-study tofacitinib dose must remain stable at 5 mg BID. The MTX dose and oral route of administration must remain stable for the 12 month duration of the sub-study. All subjects will receive open-label tofacitinib 5 mg BID throughout the sub-study without dose increase. The total number of subjects randomized will be approximately 180 (Sub-Study [Table 2](#)).

Sub-Study Table 2

Treatment Group	Double blind placebo controlled period	Number of Subjects
B	Tofacitinib 5 mg BID + Placebo	90
C	Tofacitinib 5 mg BID + Methotrexate	90

Treatment duration for subjects participating in this sub-study is approximately 12 months.

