5.4. Sub-Study Administration

All investigational products will be self-administered by the subject as specified in the dosing card. Tofacitinib should be administered orally, twice daily, approximately 12 hours apart, once in the morning and once in the evening. During the sub-study all subjects will receive a dose of 5 mg BID taking 1 tablet in the morning and 1 tablet in the evening. If a tofacitinib dose is missed and the interval to the next scheduled dose is less than 6 hours, the missed dose of tofacitinib should not be administered.

At the time of enrollment (eg, the Combined A3921092 Sub-study Switch/Baseline visit), subjects must discontinue the use of their personal (commercial) supply of MTX. MTX or its matching placebo will be provided by the Sponsor and must be administered orally once a week (the same day of the week) in a predetermined dose that may range from 7.5 mg/week to 20 mg/week. Subjects will receive the corresponding number of MTX or matching placebo 2.5 mg capsules to complete their individual preselected dose of oral MTX (Sub-Study [Table 3](#)). Subjects should be instructed to document any missed doses.

Sub-Study Table 3

Assigned Dose of MTX	Corresponding number of MTX 2.5 mg capsules or matching placebo
7.5 mg/week	3 capsules
10 mg/week	4 capsules
12.5 mg/week	5 capsules
15 mg/week	6 capsules
17.5 mg/week	7 capsules
20 mg/week	8 capsules

Subjects who are randomized to tofacitinib 5 mg BID + MTX placebo will experience a full withdrawal of MTX (eg, no tapering) at the time of randomization.

Study medications may be administered with or without food, with exception of the day of the study visits that require fasting.

Medication errors may result in the sub-study from the administration or consumption of the wrong product, by the wrong subject, at the wrong time, or at the wrong dose. Such medication errors occurring to a study participant are to be captured on the adverse event page of the CRF and on the SAE form when appropriate. In the event of a dosing error, the sponsor should be notified immediately. Whether or not the medication error is accompanied by an AE, as determined by the investigator, it is captured on an adverse event (AE) CRF

page as well as any AEs associated with the medication error (refer to [Section 8](#) of main LTE protocol).

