2.1. Study Design

This is a Phase 3, long-term, open-label extension study designed to evaluate the safety, tolerability and efficacy of tofacitinib in subjects with active PsA. Subjects with active PsA will have previously participated in randomized studies of tofacitinib. For subjects who are completing participation in a randomized study of tofacitinib, the final visit of the qualifying study can be combined with screening and baseline visit for this study. Additional assessments and inclusion/exclusion criteria are required for subjects who enroll >14 days after completing treatment in their qualifying study. In this case, a separate screening visit to determine subject eligibility is required followed by a baseline visit.

All eligible subjects from qualifying studies A3921091 and A3921125 will receive open-label tofacitinib 5 mg BID upon entry into A3921092. Subjects from A3921091 will receive first dose of study medication ≥ 1 week after last injection of study medication in that qualifying study. Tofacitinib dose may be increased to 10 mg BID at study visits if, based upon investigator's discretion, subjects receiving tofacitinib 5 mg BID would benefit from a higher dose and are not experiencing any tofacitinib-related adverse events, including abnormalities in laboratory test results that are judged to be related to tofacitinib. Tofacitinib dose may be decreased (ie, 10 mg BID to 5 mg BID) for safety reasons at any time. Treatment duration for subjects participating in the main LTE study is approximately 3 years (36 standardized 4-week months). Subjects participating in the sub-study may have up to an additional 1 year (12 standardized 4-week months) of treatment for a maximum potential total of approximately 4 years (48 standardized 4-week months).

At various timepoints in this trial, safety measurements, including physical examination, clinical laboratory tests, adverse event monitoring, electrocardiograms (ECGs) and vital signs will be performed. All subjects will be monitored for clinical evidence of PsA response to treatment. Health Outcomes Measures (ie, Patient Reported Outcomes assessments for pain, quality of life, physical function, fatigue, work limitations, health care resource utilization and health status) will also be performed at various timepoints in this trial. In addition, subjects will be monitored for serious infections, lymphadenopathy and lymphoproliferative disorder (LPD).

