8.2. Statistical Analyses

Tofacitinib dose may be increased to 10 mg BID at study visits based upon investigator's discretion. Also, tofacitinib dose may be decreased (ie, 10 mg BID to 5 mg BID) for safety

reasons at any time. Hence changes in the dose are treatment related. Consequently, descriptive statistics will be displayed for just one treatment group: the entire cohort of subjects in which tofacitinib is dosed flexibly between 5 mg and 10 mg BID.

The baseline values for the safety endpoints come from the baseline of the qualifying study for patients who enroll within 14 days of the last visit of the qualifying study. For the patients whose enrollment are out of 14-day window, their baseline values of the safety endpoints will be from the baseline visit of this study, A3921092. The baseline values for all the efficacy or health-outcome endpoints come from the baseline of the qualifying study. In addition, as a sensitivity analysis for the ACR response rates and Δ HAQ-DI, the baseline value will be the baseline visit for A3921092 for patients whose enrollment is out of 14-day window.

All analyses will use FAS (Section 5.1) or FAS with some subjects excluded from analyses for certain endpoints (Section 5.4.1) except where indicated otherwise.

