8.2.1. Analysis of Primary Endpoints

Safety analysis will include cumulative data from both the main LTE study and sub-study.

- Adverse events will be summarized according to Pfizer Data Standards (PDS).
- Incidence rate (IR) defined as the number of subjects with an event in the numerator divided by the study drug exposure in the denominator (expressed as the number of subjects with an event per 100 patient-years) will be calculated for deaths, SAEs, AEs leading to discontinuation and AEs of special interest. AEs of special interest include but may not be limited in the events listed in **Table 2** AEs of Special Interest. The event will be counted from subject's first dose to subject's last dose of study drug + 28 days. The denominator is the sum of the time to event or to subject's last dose of study drug + 28 days, whichever is earlier.

Table 2 AEs of Special Interest

Serious infections (SIs)
Herpes zoster (HZ)
Adjudicated opportunistic infections (OIs) excluding tuberculosis (TB) ^a
Hematologic events (anaemia, neutropenia, lymphopenia, and thrombocytopenia)
Adjudicated malignancies ^a
Adjudicated major adverse cardiovascular events (MACE) ^{a,b}
Adjudicated drug-induced liver injury (DILI) ^a and other hepatic events ^c
Renal events ^d
Adjudicated gastrointestinal (GI) perforations ^a
Adjudicated interstitial lung disease (ILD) ^e

Abbreviations: DILI = drug-induced liver injury; GI = gastrointestinal; HZ = herpes zoster; ILD = interstitial lung disease; MACE = major adverse cardiovascular events; MedDRA = Medical Dictionary for Regulatory Activities; OI = opportunistic infection; SI = serious infection; SMQ = Standardised MedDRA Queries; TB = tuberculosis.

a. Adjudicated by Adjudication Committees independent and external to Pfizer.

b. Components: cardiovascular death, non-fatal myocardial infarction, and non-fatal stroke.

c. Including SMQs: Hepatic failure, fibrosis, and cirrhosis, and other liver damage-related conditions; and Hepatitis, non-infectious.

d. Including Acute renal failure SMQ.

e. Adjudicated by an internal review committee.

- Safety laboratory tests will be summarized according to the PDS.

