- The summaries for laboratory tests include contingency tables (eg, normal, high, low), and descriptive statistics for change from baseline by treatment group and visit. For the FACS, the endpoints to be summarized, which are subsets of lymphocytes and are measured at baseline, and every 3 months beginning at Month 3 visit, are as follows: $CD3^+$ (% , abs), $CD3^+CD4^+$ (% , abs), $CD3^+CD8^+$ (% , abs), $CD19^+$ (% , abs), $CD16^+/CD56^+$ (% , abs). Raw values as well as percent change from baseline will be summarized with descriptive statistics by visit.

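### LTE by-visit laboratory and vital-sign tables pool sub-study data into one flexible-dose group to Month 48, so late trends are confounded by cohort selection and methotrexate withdrawal

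*SAP*

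**What the plan says.** SAP Section 2.1 sets the length of the main study: "Treatment duration for subjects participating in the main LTE study is approximately 3 years (36 standardized 4-week months"). SAP Appendix 1 nevertheless defines by-visit windows to Month 48, the last four marked "For safety endpoints summarized by visit such as laboratory value and vital signs data at a windowed visit only".

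SAP Section 8.2.1 states: "Safety analysis will include cumulative data from both the main LTE study and sub-study". Section 8.2.3 repeats this for vital signs and ECG, and Protocol Section 9 says the same of LTE safety in general. SAP Section 8.2 fixes the display as "just one treatment group: the entire cohort of subjects in which tofacitinib is dosed flexibly between 5 mg and 10 mg BID". The laboratory bullet in Section 8.2.1 asks for "descriptive statistics for change from baseline by treatment group and visit", but Section 8.2 defines only one group, so that wording does not split the data.

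The sub-study is a different treatment setting. Protocol Appendix 10, Section 3 says: "All subjects will receive open-label tofacitinib 5 mg BID throughout the sub-study without dose increase". Allocation is 1:1, and Section 5.4 says that those given MTX placebo "will experience a full withdrawal of MTX (eg, no tapering) at the time of randomization". Entry under Section 4.1 of that appendix requires 24 completed months in the LTE, oral MTX, and tofacitinib stable at 5 mg BID for at least 3 months.

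**The concern.** Change from baseline in laboratory values is a primary LTE endpoint (Protocol Section 2.2.1). Protocol Section 9.2.1 singles out transaminases, bilirubin, blood counts and creatinine. Protocol Section 1.2.3 links tofacitinib to changes in several of these tests, and Appendix 10, Section 1.2 names liver toxicity as a concern with long-term MTX. A column mean that drifts after Month 36 invites the reading that tofacitinib behaves differently with longer exposure.

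The single label hides two other explanations. First, at Month 39 everyone outside the sub-study leaves the table. That includes subjects still on 10 mg BID, those not on oral MTX, and those in countries that do not take part. Second, about half of those who remain have stopped MTX. The SAP's reason for using one group is that dose changes are treatment related. That covers investigator-led titration of tofacitinib, but not a randomized withdrawal of a second drug.

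**Working it through.** **Inputs.** Window targets and limits come from SAP Appendix 1. The Month 36 visit window of ±10 days is in Protocol Section 6.2.4. The post-treatment laboratory follow-up at 28 ± 7 days after last dose is in Protocol Sections 6.3 and 7.6.7, and the monthly creatinine retests are in Appendix 4.4. Sub-study entry at Month 24, 27, 30, 33 or 36, with visits at Months 1, 3, 6, 9 and 12, is in Protocol Appendix 10. The planned total of about 180 randomized is in Appendix 10, Section 3.

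**1. Reproduce the window grid.** Target day = 28 × month + 1. This gives 1009 for Month 36, then 1093, 1177, 1261 and 1345 for Months 39, 42, 45 and 48, all as stated. The upper limit is the midpoint between adjacent targets: (1009 + 1093)/2 = 1051, which is the stated safety limit for Month 36.

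**2. Last scheduled main-LTE visit.** 1009 + 10 = Day 1019, before Day 1051. No scheduled on-treatment main-LTE visit reaches the Month 39 window, which opens on Day 1052.

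**3. Off-treatment exceptions.** A laboratory follow-up can fall as late as 1019 + 28 + 7 = Day 1054. Monthly creatinine retests after a Day 1037 follow-up fall on Days 1065, 1093 and 1121. All of these lie in the Month 39 window. Vital signs are not scheduled at the LTE follow-up visit, so the exception does not apply to them.

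**4. Map sub-study visits to LTE windows.** Target day = 28 × (entry month + sub-study month) + 1.

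| Entry | +3 | +6 | +9 | +12 |
|---|---|---|---|---|
| Month 24 | 27 | 30 | 33 | 36 |
| Month 27 | 30 | 33 | 36 | 39 |
| Month 30 | 33 | 36 | 39 | 42 |
| Month 33 | 36 | 39 | 42 | 45 |
| Month 36 | 39 | 42 | 45 | 48 |

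The sub-study Month 1 visit normally shares a window with the entry visit and loses under the closest-to-target rule. For Month 24 entrants it is at Day 701, against a visit at the target Day 673. Sub-study values therefore enter from about the Month 27 window.

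**5. Count.** Entry cohorts contributing a quarterly sub-study visit at Months 27, 30, 33, 36, 39, 42, 45 and 48 number 1, 2, 3, 4, 4, 3, 2 and 1. Ten of the 20 cohort-visits fall at or before Month 36.

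**6. Subjects per window.** These depend on entry timing, which the documents do not give. All rows assume 180 entrants and no dropout.

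| Entry pattern | Month 39 | Month 42 | Month 45 | Month 48 |
|---|---|---|---|---|
| Even, 180/5 = 36 per visit | 144 | 108 | 72 | 36 |
| All at Month 24 | 0 | 0 | 0 | 0 |
| All at Month 36 | 180 | 180 | 180 | 180 |

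**7. Effect on a column mean.** If stopping MTX shifts a laboratory mean by d, 1:1 allocation moves a column made up only of sub-study data by about d/2, with no change in the effect of tofacitinib. The documents give no value for d, so this shows the mechanism and not its size.

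**The case against.** The pooling is declared in both documents, the LTE analyses are descriptive, and no hypothesis is tested. SAP Appendix 6, Section 7.2.3 already summarizes sub-study safety by randomized arm, and an MTX-withdrawal effect should be looked for there. MTX change is also not unique to the sub-study, because Protocol Section 5.6.1 lets background DMARDs be adjusted, tapered or stopped during the main LTE. All of this stands and limits the weight of the point. It does not make the single label accurate. Nor can the by-arm tables be used to correct the LTE columns, because they use another baseline (SAP Appendix 6, Section 5) and count days from first sub-study dose (Section 7.4).

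A reader might infer that every value after Month 36 is from the sub-study. That holds for scheduled on-treatment values, but off-treatment main-LTE laboratory follow-ups can fall in the Month 39 window. The documents do not show whether the sponsor's data standards would exclude them.

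A reader might also infer that late trends show a change of treatment. The documents do not support that. Entrants are already stable on 5 mg BID, so entry itself changes no tofacitinib dose. The MTX arm continues its pre-entry dose (Appendix 10, Section 5.1), and only the placebo arm changes treatment. The larger break at Month 39 is in who remains in the table.

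**Conclusion.** The point holds as one of confounding and labelling. The LTE by-visit laboratory and vital-sign tables mix sub-study values into a flexible-dose group from about the Month 27 window. In the Month 39 to 48 windows, they consist entirely of sub-study data as far as scheduled on-treatment values go. A late trend in these columns cannot separate longer exposure from cohort selection and MTX withdrawal.

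The window arithmetic follows from the documents. The number affected does not: after Month 36 it runs from no scheduled values (all entering at Month 24) to all quarterly sub-study visits (all entering at Month 36). The 144/108/72/36 pattern is one scenario, with even entry and no dropout. No shift in any laboratory mean has been shown. The change is worth making because it is cheap and the affected laboratory summaries serve a primary endpoint.

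**What to change.** Keep the cumulative LTE safety analysis that the protocol specifies. In SAP Sections 8.2.1 and 8.2.3 and Appendix 1, state that by-visit laboratory, vital-sign and ECG tables carry additional columns from first sub-study dose (Month 27 window on): main LTE, sub-study + MTX and sub-study + placebo. Show N per source in each window, and do not label the sub-study columns as flexibly dosed. Adverse events and incidence rates stay cumulative.

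Restricting these tables to main-LTE data is not advised. It would depart from the cumulative analysis in Protocol Section 9. It would also remove oral-MTX, 5 mg BID subjects selectively from Month 27 on, which is a cohort shift of its own.

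The cost is SAP wording and table shells, with no new data. The downside is wider tables, with small N in the late columns.
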